4. REGISTRATION PROCEDURES

4.1 Investigator and Research Associate Registration with CTEP

Food and Drug Administration (FDA) regulations and National Cancer Institute (NCI) policy require all individuals contributing to NCI-sponsored trials to register and to renew their registration annually. To register, all individuals must obtain a Cancer Therapy Evaluation Program (CTEP) Identity and Access Management (IAM) account at <https://ctepcore.nci.nih.gov/iam>. In addition, persons with a registration type of Investigator

(IVR), Non-Physician Investigator (NPIVR), or Associate Plus (AP) (*i.e.*, clinical site staff requiring write access to Oncology Patient Enrollment Network (OPEN), Rave, or acting as a primary site contact) must complete their annual registration using CTEP's web-based Registration and Credential Repository (RCR) at <https://ctepcore.nci.nih.gov/rcr>.

RCR utilizes five person registration types.

- IVR: MD, DO, or international equivalent,
- NPIVR: advanced practice providers (*e.g.*, NP or PA) or graduate level researchers (*e.g.*, PhD),
- AP: clinical site staff (*e.g.*, RN or CRA) with data entry access to CTSU applications (*e.g.*, Roster Update Management System [RUMS], OPEN, Rave,),
- Associate (A): other clinical site staff involved in the conduct of NCI-sponsored trials, and
- Associate Basic (AB): individuals (*e.g.*, pharmaceutical company employees) with limited access to NCI-supported systems.

RCR requires the following registration documents:

Documentation Required	IVR	NPIVR	AP	A	AB
FDA Form 1572	✓	✓			
Financial Disclosure Form	✓	✓	✓		
NCI Biosketch (education, training, employment, license, and certification)	✓	✓	✓		
GCP training	✓	✓	✓		
Agent Shipment Form (if applicable)	✓				
CV (optional)	✓	✓	✓		

An active CTEP-IAM user account and appropriate RCR registration is required to access all CTEP and Cancer Trials Support Unit (CTSUS) websites and applications. In addition, IVRs and NPIVRs must list all clinical practice sites and Institutional Review Boards (IRBs) covering their practice sites on the FDA Form 1572 in RCR to allow the following:

- Addition to a site roster,
- Assign the treating, credit, consenting, or drug shipment (IVR only) tasks in OPEN,
- Act as the site-protocol Principal Investigator (PI) on the IRB approval, and
- Assign the Clinical Investigator (CI) role on the Delegation of Tasks Log (DTL).

In addition, all investigators act as the Site-Protocol PI, consenting/treating/drug shipment, or as the CI on the DTL must be rostered at the enrolling site with a participating organization (*i.e.*, Alliance).

Additional information is located on the CTEP website at

<https://ctep.cancer.gov/investigatorResources/default.htm>. For questions, please contact the RCR Help Desk by email at [contact].

4.2 Site Registration

This study is supported by the NCI Cancer Trials Support Unit (CTSU).

IRB Approval

Sites participating with the NCI Central Institutional Review Board (NCI CIRB) must submit the Study Specific Worksheet for Local Context (SSW) to the CIRB using IRBManager to indicate their intent to open the study locally. The NCI CIRB's approval of the SSW is automatically communicated to the CTSU Regulatory Office, but sites are required to contact the CTSU Regulatory Office at [contact] to establish site preferences for applying NCI CIRB approvals across their Signatory Network. Site preferences can be set at the network or protocol level. Questions about establishing site preferences can be addressed to the CTSU Regulatory Office by emailing the email address above or calling [name].

Sites using their local IRB or REB must submit their approval to the CTSU Regulatory Office using the Regulatory Submission Portal located in the Regulatory section of the CTSU website. Acceptable documentation of local IRB/REB approval includes:

- Local IRB documentation,
- IRB-signed CTSU IRB Certification Form, and/or
- Protocol of Human Subjects Assurance Identification/IRB Certification/Declaration of Exemption Form.

In addition, the Site-Protocol PI (*i.e.*, the investigator on the IRB/REB approval) must meet the following five criteria to complete processing of the IRB/REB approval record:

- Holds an Active CTEP status,
- Rostered at the site on the IRB/REB approval (*applies to US and Canadian sites only*) and on at least one participating roster,
- If using NCI CIRB, rostered on the NCI CIRB Signatory record,
- Includes the IRB number of the IRB providing approval in the Form FDA 1572 in the RCR profile, and
- Holds the appropriate CTEP registration type for the protocol.

Additional Requirements

Additional requirements to obtain an approved site registration status include:

- An active Federalwide Assurance (FWA) number,
- An active roster affiliation with the Lead Protocol Organization (LPO) or a Participating Organization, and
- Compliance with all protocol-specific requirements (PSRs).

4.2.1 Downloading Regulatory Documents

Download the site registration forms from the protocol-specific page located on the CTSU members' website. Permission to view and download this protocol and its supporting documents is restricted based on person and site roster assignment. To participate, the institution and its associated investigators and staff must be associated with the LPO or a Participating Organization on the protocol.

- Log on to the CTSU members' website (<https://www.ctsuo.org>) using your CTEP-IAM username and password,
- Click on *Protocols* in the upper left of your screen
 - Enter the protocol number in the search field at the top of the protocol tree, or
 - Click on the By Lead Organization folder to expand, then select *LAO-NCI*, and protocol number *10398*,
- Click on *Documents*, select *Site Registration*, and download and complete the forms provided. (Note: For sites under the CIRB initiative, IRB data will load automatically to the CTSU as described above.)

4.2.2 Protocol Specific Requirements For P10398 Site Registration

Upon site registration approval in RSS, the enrolling site may access OPEN to complete enrollments. The enrolling site will select their credentialed provider treating the subject in the OPEN credentialing screen, and may need to answer additional questions related to treatment in the eligibility checklist.

- A teleconference training led by the Coordinating Center is required for each participating site prior to the site's initial activation in RSS.

4.2.3 Submitting Regulatory Documents

Submit required forms and documents to the CTSU Regulatory Office via the Regulatory Submission Portal on the CTSU website.

To access the Regulatory Submission Portal, log on to the CTSU members' website → Regulatory → Regulatory Submission.

Institutions with patients waiting that are unable to use the Regulatory Submission Portal should alert the CTSU Regulatory Office immediately at [name] in order to receive further instruction and support.

Delegation of Tasks Log (DTL)

Each site must complete a protocol-specific DTL using the DTL application in the Delegation Log section on the CTSU members' website. The Clinical Investigator (CI) is required to review and electronically sign the DTL prior to the site receiving an Approved site registration status

and enrolling patients to the study. To maintain an approved site registration status the CI must re-sign the DTL at least annually and when a new version of the DTL is released; and activate new task assignments requiring CI sign-off. Any individual at the enrolling site on a participating roster may initiate the site DTL. Once the DTL is submitted for CI approval, only the designated DTL Administrators or the CI may update the DTL. Instructions on completing the DTL are available in the Help Topics button in the DTL application and include a Master Task List, which describes DTL task assignments, CI signature, and CTEP registration requirements.

4.2.4 Checking Site Registration Status

You can verify your site's registration status on the members' side of the CTSU website.

- Log on to the CTSU members' website
- Click on *Regulatory* at the top of your screen
- Click on *Site Registration*
- Enter your 5-character CTEP Institution Code and click on Go

Note: The status shown only reflects institutional compliance with site registration requirements as outlined above. It does not reflect compliance with protocol requirements for individuals participating on the protocol or the enrolling investigator's status with the NCI or their affiliated networks.

4.3 Patient Registration

4.3.1 OPEN / IWRS

The Oncology Patient Enrollment Network (OPEN) is a web-based registration system available on a 24/7 basis. OPEN is integrated with CTSU regulatory and roster data and with the Lead Protocol Organization (LPOs) registration/randomization systems or Theradex Interactive Web Response System (IWRS) for retrieval of patient registration/randomization assignment. OPEN will populate the patient enrollment data in NCI's clinical data management system, Medidata Rave.

Requirements for OPEN access:

- A valid CTEP-IAM account.
- To perform enrollments or request slot reservations: Be on an LPO roster, ETCTN Corresponding roster, or Participating Organization roster with the role of Registrar. Registrars must hold a minimum of an AP registration type.
- If a DTL is required for the study, the registrar(s) must hold the OPEN Registrar task on the DTL for the site.
- Have an approved site registration for a protocol prior to patient enrollment.

To assign an Investigator (IVR) or Non-Physician Investigator (NPIVR) as the treating, crediting, consenting, drug shipment (IVR only), or receiving investigator for a patient transfer in

OPEN, the IVR or NPIVR must list the IRB number used on the site's IRB approval on their Form FDA 1572 in RCR. If a DTL is required for the study, the IVR or NPIVR must be assigned the appropriate OPEN-related tasks on the DTL.

Prior to accessing OPEN, site staff should verify the following:

- Patient has met all eligibility criteria within the protocol stated timeframes, and
- All patients have signed an appropriate consent form and HIPAA authorization form (if applicable).

Note: The OPEN system will provide the site with a printable confirmation of registration and treatment information. Please print this confirmation for your records.

Access OPEN at <https://open.ctsuh.org> or from the OPEN link on the CTSU members' website. Further instructional information is in the OPEN section of the CTSU website at <https://www.ctsuh.org> or <https://open.ctsuh.org>. For any additional questions, contact the CTSU Help Desk at [name] or [contact].

Patient enrollment for this study will be facilitated using the Slot Reservation System in conjunction with the registration system in OPEN. Prior to discussing protocol entry with the patient, all site staff must use the IWRS Slot Reservation System to ensure that a slot on the protocol is available to the patient. Once a slot reservation confirmation is obtained, site staff may then proceed to enroll the patient to this study. Slots can be reserved for a maximum of 14 calendar days.

The OPEN system will provide the site with a printable confirmation of registration and treatment information. Please print this confirmation for your records.

Following registration, patients should begin protocol treatment within 8 days. Issues that would cause treatment delays should be discussed with the Principal Investigator.

4.3.2 OPEN/IWRS Questions?

Further instructional information on OPEN is provided on the OPEN link of the CTSU website at <https://www.ctsuh.org> or at <https://open.ctsuh.org>. For any additional questions contact the CTSU Help Desk at [name] or [contact].

Theradex has developed a Slot Reservations and Cohort Management User Guide, which is available on the Theradex website: <http://www.theradex.com/clinicalTechnologies/?National-Cancer-Institute-NCI-11>. This link to the Theradex website is also on the CTSU website OPEN tab. For questions about the use of IWRS for slot reservations, contact the Theradex Helpdesk at [contact] or Theradex main number [contact]; [contact].

4.4 General Guidelines

Following registration, patients should begin protocol treatment within 8 days. Issues that would cause treatment delays should be discussed with the Principal Investigator. If a patient does not receive protocol therapy following registration, the patient's registration on the study may be canceled. The Study Coordinator should be notified of cancellations as soon as possible.

5. TREATMENT PLAN

This is a multicenter open-label phase 2 trial evaluating atezolizumab in adult subjects ≥ 18 years of age and in pediatric/adolescent subjects ≥ 2 years of age with advanced CCS or CS. Patients will be divided into cohorts based on histology upon enrollment. There will be three cohorts: histologically confirmed CCS (or EWSR1 translocation), conventional CS (grade 2 or 3), and dedifferentiated CS.

Patient evaluations will be performed throughout the study as described below. Baseline history, physical examination, laboratory evaluations, urinalysis, and EKG are to be conducted within 8 days prior to the start of protocol therapy. If protocol therapy is started within 8 days of these eligibility screening evaluations (see Section [3.3](#)), values from the screening evaluations may be used as baseline measurements; if >8 days have passed since the screening evaluations, the medical history, physical examination, laboratory evaluations, urinalysis, and EKG must be repeated prior to starting protocol therapy. Baseline imaging scans and ECHO must be done within 28 days prior to the start of protocol therapy.

History and physical examination will be done within 8 days of Day 1 of all cycles. Labs (serum chemistries and CBC with differential) will be performed at baseline as described above, on Cycle 1 Day 15 [± 1 day], and then up to 3 days before the start of each subsequent cycle (LDH and protein do not need to be checked again after baseline). TSH will be checked at baseline (within 8 days of Cycle 1 Day 1) and then up to 3 days before the start of each subsequent cycle. EKG will be repeated as clinically indicated after the baseline measurement described above.

Patients will have a CT scan at baseline (within 28 days prior to start of protocol therapy). Patients will undergo a CT scan and be re-evaluated for response at the end of Cycle 3 and every two cycles thereafter (every 3 cycles for patients on study for >1 year; every 4 cycles for patients on study for >2 years). Given the concern of pseudoprogression ("tumor flare"), patients that are clinically well may continue on therapy following RECIST progression if they meet the criteria outlined in Section 11.4.

Research biopsies (mandatory for adult patients at all sites) and blood samples for PD studies (mandatory for patients ≥ 12 years of age) will be collected as described in Section [9.2](#) and Section [9.3](#).

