6. DOSING DELAYS/DOSE MODIFICATIONS

6.1 General AE Management and Dose Modification Guidelines

There will be no dose reduction for atezolizumab in this study.

Patients may temporarily suspend study treatment for up to 84 days (12 weeks) beyond the scheduled date of delayed infusion if study drug-related toxicity requiring dose suspension is experienced. If atezolizumab is held because of AEs for >84 days beyond the scheduled date of infusion, the patient will be discontinued from atezolizumab and will be followed for safety and efficacy as specified in this protocol. If the AE resolves within 84 days and the patient is receiving corticosteroid therapy for the event, atezolizumab may be held for longer than 84 days (up to 4 weeks) in order to allow tapering of the steroid dose to ≤ 10 mg oral prednisone or equivalent.

Dose interruptions for reasons other than toxicity, such as surgical procedures, may be allowed. The acceptable length of interruption will be at the discretion of the study PI in consultation with CTEP.

The primary approach to grade 1 to 2 irAEs is supportive and symptomatic care with continued treatment with atezolizumab; for higher-grade irAEs, atezolizumab should be withheld and oral and/or parenteral steroids administered. Recurrent grade 2 irAEs may also mandate withholding atezolizumab or the use of steroids. Assessment of the benefit risk balance should be made by the investigator, with consideration of the totality of information as it pertains to the nature of the toxicity and the degree of clinical benefit a given patient may be experiencing prior to further administration of atezolizumab. Atezolizumab should be permanently discontinued in patients with life threatening irAEs.

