10. STUDY CALENDAR

Eligibility screening evaluations (see Section [3.3](#)) are to be conducted within 8 days prior to patient enrollment, with the exception of informed consent, echocardiogram (ECHO), and imaging, which must be done within 28 days prior to patient enrollment. Baseline history, physical examination, laboratory evaluations, and EKG are to be conducted within 8 days prior to the start of protocol therapy. If protocol therapy is started within 8 days of the eligibility screening evaluations, values from the screening evaluations may be used as baseline measurements; if >8 days have passed since the screening evaluations, the medical history, physical examination, laboratory evaluations, and EKG must be repeated prior to starting protocol therapy. Baseline imaging scans and ECHO must be done within 28 days prior to the start of protocol therapy.

Each cycle is 21 days (± 3 days due to scheduling conflicts). The start of a new cycle may be delayed up to 2 weeks to accommodate scheduling conflicts and other unexpected events. In the event that the patient's condition is deteriorating, laboratory evaluations should be repeated within 48 hours prior to initiation of the next cycle of therapy.

	Pre-Study Screening	Cycle 1 Week 1	Cycle 1 Week 2	Cycle 1 Week 3	Cycle 2 Week 1	Cycle 3 Week 1	Cycles 4+ Week 1	Off Treatment
Atezolizumab ^a		A			A	A	A	
Informed consent	X							
Demographics	X							
Medical history	X	X ^j						
Concurrent meds	X	X-----X						
Physical exam ^b	X	X ^j			X	X	X	X
Vital signs	X	X ^j			X	X	X	X
Height	X							
Weight	X	X ^j			X	X	X	X
Performance status	X	X ^j			X	X	X	X
CBC w/diff, plts ^c	X	X ^j			X	X	X	X
Serum chemistry ^c	X	X ^j			X	X	X	X
TSH ^d	X	X ^j			X	X	X	X
EKG ^e	X	X ^j						
Echocardiogram ^e	X	X ^j						
Adverse event evaluation		X-----X						X
Tumor measurements ^f	X	Tumor measurements are repeated every 6 weeks. Documentation (radiologic) must be provided for patients removed from study for progressive disease.						X
B-HCG ^g	X	X ^j			X	X	X	
Biopsy ^h		X				X ^h		X ⁱ
Blood for PD ^k		X		X ^k	X	X	X	X
Blood for genetics ^l		X	Blood for ctDNA analysis at C2D1, at the time of any biopsy, at the first two restagings (end of C3 and end of C5), and every two restaging visits after that (e.g., C9, C13, etc.)					X

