a: Atezolizumab dose as assigned; adults ≥ 18 years at 1200 mg IV and in pediatric/adolescents ≥ 2 years at 15 mg/kg (max single dose=1200 mg); drug will be administered once on Day 1 only of each cycle. Each cycle is 21 days (± 3 days). Start of new cycle may be delayed up to 2 weeks to accommodate scheduling conflicts.

b: History and physical at baseline and up to 8 days before the start of each subsequent cycle.

c: CBC w/diff, plts, and serum chemistry (ACTH, albumin, alkaline phosphatase, AM cortisol, amylase, bicarbonate, total bilirubin, BUN, calcium, chloride, creatinine, glucose, LDH, lipase, phosphorus, potassium, pregnancy test per institutional standard at each participating site, total protein, SGOT [AST], SGPT [ALT], sodium, free T4) at baseline and then up to 3 days before the start of each subsequent cycle. After baseline, amylase, LDH, lipase, protein, and free T4 do not need to be checked.

d: TSH levels at baseline and then up to 3 days before the start of each subsequent cycle.

e: Baseline and as indicated.

f: CT scan or other imaging test at baseline, at the end of Cycle 3, and every two cycles thereafter (every 3 cycles for patients on study for >1 year; every 4 cycles for patients on study for >2 years).

g: Serum or urine pregnancy test (women of childbearing potential) within 8 days prior to enrollment. If

clinically indicated, serum or urine pregnancy test is required for women of childbearing potential ≤ 8 days before the start of each treatment cycle [per institutional standard at each participating site]; outside lab results are acceptable.

- h: Adult patients (≥ 18 years of age; mandatory at all sites), at baseline and prior to C3D1 (± 3 days) or sooner if there is clinical evidence that the patient is responding to drug, as described in Section [9.2.1](#).
- i: One optional tumor biopsy may be collected following progression or a 10-19% increase in tumor volume at restaging, as described in Section [9.2.1](#).
- j: Eligibility screening results may be used for these baseline measurements if conducted within 8 days (for medical history, physical exam, CBC, serum chemistry, TSH, and EKG) or 28 days (for ECHO) prior to the start of protocol therapy. See Sections [3.3](#) and [5](#).
- k: **At NCI only:** blood for ImmunoPD (mandatory from patients ≥ 12 years of age) on C1D1, C1D15 (optional), day one of each cycle, and at restaging follow up or progression as described in Section [9.3](#).

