11. MEASUREMENT OF EFFECT

11.1 Antitumor Effect – Solid Tumors

Patients should be re-evaluated for response at the end of Cycle 3 (before Cycle 4), and at the end of every two cycles thereafter (before every even-numbered cycle). Restaging scans may be performed less frequently for patients on study for more than 1 year (every three cycles for patients on study for more than 1 year; every four cycles for patients on study more than 2 years). Confirmatory scans should also be obtained ≥ 4 weeks following initial documentation of objective response.

Response and progression will be evaluated in this study using the international criteria proposed by the revised Response Evaluation Criteria in Solid Tumors (RECIST) guideline (version 1.1) [59]. Changes in the largest diameter (unidimensional measurement) of the tumor lesions and the shortest diameter in the case of malignant lymph nodes are used in the RECIST criteria.

Patients that are clinically well may continue on therapy following RECIST progression with new lesions or increase in target lesions, provided the criteria in Section [11.4](#) are met.

Response will also be explored using iRECIST (see Section [11.3](#)). Increasing clinical experience indicates that traditional response criteria such as RECIST may not be sufficient to fully characterize activity in the new era of target therapies and/or biologics. In studies with therapeutic antibodies, complete response, partial response, or stable disease has been shown to occur after an increase in tumor burden, characterized by progressive disease by traditional response criteria. Therefore, conventional response criteria may not adequately assess the activity of immunotherapeutic agents because progressive disease (by initial radiographic evaluation) does not necessarily reflect therapeutic failure. Long-term effect on the target disease must also be captured. The iRECIST criteria, by incorporating specific response patterns

that have been observed with immunotherapeutic agents, have been developed to address these issues and provide standardized response criteria for use with immunotherapy [60].

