11.2.6 Progression-Free Survival

PFS is defined as the duration of time from start of treatment to time of progression or death, whichever occurs first.

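### Routine restaging is counted mostly in cycles, so a permitted drug hold can also postpone the next scan and date progression later; the calendar row says every 6 weeks and must be reconciled

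*Combined protocol and SAP*

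**What the plan says.** Four places count routine restaging in completed cycles.

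- Section 5: "Patients will undergo a CT scan and be re-evaluated for response at the end of Cycle 3 and every two cycles thereafter".
- Section 11.1: "Patients should be re-evaluated for response at the end of Cycle 3 (before Cycle 4), and at the end of every two cycles thereafter". It adds that these scans come before the even-numbered cycles.
- Section 10, footnote f: "CT scan or other imaging test at baseline, at the end of Cycle 3, and every two cycles thereafter".
- The schema gives the same schedule. All four lengthen the interval to three cycles after one year on study and four cycles after two years.

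The tumor measurement row in Section 10, to which footnote f belongs, uses calendar time: "Tumor measurements are repeated every 6 weeks".

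The plan lets cycles be delayed. Section 6.1: "Patients may temporarily suspend study treatment for up to 84 days (12 weeks) beyond the scheduled date of delayed infusion". It permits up to 4 further weeks for steroid taper, and interruptions for other reasons, such as surgery, at the study PI's discretion in consultation with CTEP. Section 10: "The start of a new cycle may be delayed up to 2 weeks to accommodate scheduling conflicts".

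Section 11.2.6 sets the exposed endpoint: "PFS is defined as the duration of time from start of treatment to time of progression or death, whichever occurs first". Section 11.2.5 ends duration of response (DOR) at the first objectively documented recurrence or progression. Neither section has a rule for a late or missed scan. Section 13.3, on secondary endpoints, deals with biopsy pairs and exploratory evaluations and gives no analysis method for PFS or DOR.

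**The concern.** Progression found by imaging is dated when it is imaged. If the scan schedule stops with the drug, the assessment interval depends on treatment delivery. Patients whose drug is held, mainly but not only for toxicity, are then looked at less often, and their progression can be recorded later than that of an undelayed patient with the same disease course. PFS is biased upward in these patients. So is DOR when the hold falls after a response has been documented. The plan has no analysis rule to compensate, and scans not taken cannot be recovered afterwards. Blood draws for ctDNA that are tied to restaging visits (Section 9.3.1.1) slip with the scans.

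**Working it through.** **1. The plan's own design figures.** Section 13.1 stops a cohort at 0 responses in 9 and calls it positive at 3 or more in 17. With response probability p:

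- Early stopping = (1 − p)^9. At p = 0.05 this is 0.95^9 = 0.630 (stated: at least .63).
- Probability of a positive result = sum over x = 1 to 9 of P(Bin(9, p) = x) × P(Bin(8, p) ≥ 3 − x). At p = 0.25 this is 0.812 (stated: at least 81%). At p = 0.05 it is 0.0466, so a negative result has probability 0.953 (stated: at least .95).

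These figures reproduce and contain no scan-timing term. The scan schedule does not alter them.

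**2. Inputs for the scan schedule.** A cycle is 21 days (Section 10). The maximum toxicity hold under Section 6.1 is 84 days = 12 weeks. Reading the taper allowance as 4 weeks on top, the maximum is 84 + 28 = 112 days = 16 weeks.

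**3. Undelayed schedule.** First scan: 3 × 21 = 63 days = week 9. Interval: 2 × 21 = 42 days = 6 weeks. Scans fall at weeks 9, 15, 21 and 27. The 6-week row therefore matches the later intervals but not the first scan.

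**4. One hold, cycle wording applied literally.**

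| Hold | Scans for Cycles 3, 5, 7, 9 (week) | Stretched interval |
|---|---|---|
| None | 9, 15, 21, 27 | none |
| 84 days, before Cycle 4 or 5 | 9, 27, 33, 39 | 6 becomes 18 weeks |
| 112 days, before Cycle 4 or 5 | 9, 31, 37, 43 | 6 becomes 22 weeks |
| 84 days, before Cycle 2 or 3 | 21, 27, 33, 39 | first scan 9 becomes 21 |
| 112 days, before Cycle 2 or 3 | 25, 31, 37, 43 | first scan 9 becomes 25 |

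After one year the interval of 9 weeks becomes 9 + 12 = 21 or 9 + 16 = 25. After two years, 12 becomes 24 or 28. A single 2-week scheduling delay turns 6 weeks into 8.

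**5. Effect on the progression date.** The largest shift occurs when disease progresses just after the week 9 scan. It is dated week 27 or 31 instead of week 15, which is 12 or 16 weeks later.

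As an illustration, assume progression is uniform over the stretched gap. Mean detection delay is half the gap: 18/2 = 9 weeks or 22/2 = 11 weeks. With calendar scans every 6 weeks across the same span it is 3 weeks for the 18-week gap. For the 22-week gap, counting a scan at its end, it is (18 × 3 + 4 × 2)/22 = 2.8 weeks. The mean extra delay is about 6 or 8 weeks.

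**6. What cannot be computed.** The documents give neither a hold rate nor a distribution of hold lengths for this population, so no change in median PFS follows.

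**The case against.** **The calendar row already uses weeks.** If the 6-week row governs, a hold moves nothing. This stands: it cannot be said that the plan uses cycles throughout. But the row's own footnote counts cycles, as do three other places, and the row disagrees with a first scan at the end of Cycle 3. Reconciling the row to the majority wording would make the slippage the rule, so the two matters should be settled together.

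**Some scans are timed in weeks.** Section 11.1 asks for confirmation at least 4 weeks after a first response. Sections 11.3 and 11.4 set 4 to 8 weeks after unconfirmed or RECIST progression. These scans are not affected. Section 11.3 also asks for assessments to continue until unequivocal progression, but sets no interval. The gap concerns routine scans only.

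**Holds are not the same as immune toxicity.** A reader might infer that delay falls on exactly the patients with immune toxicity. The documents do not support that. Section 6.1 generally continues treatment through grade 1 to 2 events; many grade 3 to 4 events in Section 6.2 lead to permanent discontinuation; scheduling and surgical delays also move scans. However, several Section 6.2 tables do hold drug at grade 2 (for example pulmonary, colitis and renal), so toxicity holds are a planned part of the trial.

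**Stage 1.** A reader might infer that held patients lose scans inside the 9-month futility window, six falling to four (weeks 9, 15, 21, 27, 33, 39 against 9, 27, 33, 39). That window runs from the ninth patient's enrollment, so the count fits at most that patient; earlier patients have longer. Treatment may start up to 8 days after registration, which can push the week 39 scan outside the window and leave five against three. No effect on the futility decision has been shown.

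**Size.** The hold lengths used are maxima. The nearest figure in the documents is 13.7% with treatment-related grade 3 or 4 events in the first-in-human study (Section 2.3.4.3), or 0.137 × 17 = 2.3 patients per cohort. It is a poor proxy, since it omits grade 2 holds and includes permanent stops, but it suggests that few patients per cohort would be affected. The plan makes no comparison by toxicity.

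**Conclusion.** The point holds for PFS and DOR. Under the cycle wording, a hold at the Section 6.1 maximum stretches a 6-week interval to 18 to 22 weeks, or moves the first scan from week 9 to week 21 to 25. No late-scan rule corrects the resulting dates. The individual shift is at most 12 to 16 weeks under Section 6.1; some Section 6.2 footnotes allow a longer hold without a fixed ceiling. The mean extra delay of about 6 to 8 weeks applies only to a patient with a maximum hold and rests on uniform progression. An unscheduled scan, or death, could date the event earlier.

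The bias is upward and concentrated in held patients. Its size for a cohort is unknown, and the endpoints are secondary in single-arm cohorts. The primary response rule and its operating characteristics stand. The change is worth making because it is cheap and the lost assessments cannot be recovered later.

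**What to change.** When the tumor measurement row is reconciled with footnote f, state the routine restaging interval in weeks from Cycle 1 Day 1, with a visit window, and say that it applies whether or not doses are delayed or interrupted. Use the same sentence in the schema, Section 5, Section 10 (row and footnote f) and Section 11.1. For reference, the present cycle counts in an undelayed patient amount to week 9, then every 6 weeks, every 9 weeks after one year and every 12 weeks after two years. The sponsor must settle which interval is intended. Tie the restaging ctDNA draws in Section 9.3.1.1 and the calendar to the same visits.

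The cost is protocol wording. No dose, hold or stopping rule changes, and no scans are added beyond those planned for an undelayed patient. The small downside is that a scan during a hold may not coincide with an infusion visit.
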